#### **8.3.4.1      Emergency Medical Contacts**

To ensure the safety of study participants, access to the Medical monitors is available 24 hours a day 7 days a week. Details will be available separately.

#### **8.3.5            Pregnancy**

Female participants of childbearing potential will be instructed to immediately inform the Investigator if they become pregnant during the study or within 90 days after the final dose of study treatment

Male participants will be instructed through the Informed Consent Form to immediately inform the Investigator if their female partner becomes pregnant during the study or within 90 days after the final dose of study treatment.

If a pregnancy is reported, the Investigator should inform the Sponsor within 24 hours of learning of the pregnancy and should follow the pregnancy reporting process as detailed in [Appendix 5](#).

Abnormal pregnancy outcomes (e.g., spontaneous abortion, fetal death, stillbirth, congenital anomalies, ectopic pregnancy) are considered SAEs ([Appendix 5](#)).

#### **8.3.6            Adverse Events of Special Interest**

AESIs are required to be reported by the Investigator to the Sponsor immediately (i.e., no more than 24 hours after learning of the event; see [Appendix 2](#) for reporting instructions).

AESIs for this study include the following:

- Cases of an elevated ALT or AST in combination with either an elevated bilirubin or clinical jaundice, as defined in [Appendix 3](#).
- Suspected transmission of an infectious agent by the study treatment, as defined below:

Any organism, virus, or infectious particle (e.g., prion protein transmitting transmissible spongiform encephalopathy), pathogenic or non-pathogenic, is considered an infectious agent. A transmission of an infectious agent may be suspected from clinical symptoms or laboratory findings that indicate an infection in a participant exposed to a medicinal product. This term applies only when a contamination of the study treatment is suspected.

- Serious complications of DM, including but not limited to, amputations, ulcers, and/or DM-related surgeries
- Sight-threatening AEs: an AE is considered to be sight-threatening and should be reported expeditiously if it meets one or more of the following criteria:
  - Causes a decrease of  $\geq 30$  letters in VA score (compared with the last assessment of VA prior to the most recent assessment) lasting more than 1 hour
  - Requires surgical or medical intervention (i.e., conventional surgery, vitrectomy, vitreous tap or biopsy with IVT injection of anti-infective treatments, or laser or retinal cryopexy with gas or a medication) to prevent permanent loss of sight
  - Is associated with severe intraocular inflammation (i.e., endophthalmitis, Grade 4+ anterior chamber cells/flare; see [Appendix 6](#) for intraocular grading scales).

All of the above listed sight-threatening AEs should be reported as SAEs (see [Appendix 2](#)), listing the underlying cause (if known) of the event as the primary event term.

### **8.3.7 Disease-Related Events and/or Disease-Related Outcomes Not Qualifying as AEs or SAEs**

Natural progression of the disease may include development of DME, worsening of DME (if present at baseline), development of ASNV or development of PDR. These events are thus not considered AEs. However, it is upon the Investigator's opinion to determine if the above events are to be considered AEs. In this case they will be reported following the usual procedure (see [Appendix 2](#) for further details on AE reporting).

### **8.3.8 Management of Specific Adverse Events**

This section does not apply to study BP41321.

## **8.4 TREATMENT OF OVERDOSE**

Study treatment overdose is the accidental administration of a drug in a quantity that is higher than the assigned dose. An overdose or incorrect administration of study treatment is not an AE unless it results in untoward medical effects (see Section 5 and 5.2 of [Appendix 2](#) for further details). For RG7774 no specific information regarding treatment of overdose is currently available.

Decisions regarding dose-interruptions or modifications (if applicable) will be made by the Investigator in consultation with the Medical Monitor based on the clinical evaluation of the participant.

In the event of an overdose, no further RG7774 should be administered and the Investigator should:

1. Contact the Sponsor's Medical Monitor immediately.
2. Closely monitor the participant for AE/SAE and laboratory abnormalities until resolved.
3. Obtain a blood sample for PK analysis within 24 hours from the date of the final dose of study treatment, if requested by the Medical Monitor (determined on a case-by-case basis).
4. Document the quantity of the excess dose, as well as the duration of the overdose, in the eCRF.

For further information see the [Investigator's Brochure](#).

## **8.5 PHARMACOKINETICS**

Blood samples for pharmacokinetic determination of plasma concentrations of RG7774 (and its metabolite[s] as appropriate) will be collected as specified in the Schedule of Assessments Table.

The actual date and time of the PK blood sampling needs to be precisely entered into the corresponding eCRF section.

Plasma concentrations of RG7774 will be measured by a specific and validated LC-MS/MS method. Plasma concentrations of RG7774-derived metabolite(s) may be measured (as appropriate) for exploratory metabolite(s) quantification purposes, with the use of non-validated LC-MS/MS method(s). Any residual material from blood PK samples may be used for additional exploratory biomarker profiling, identification, assay development purposes, and assay validation or compound-related assays after the mentioned intended use. All PK samples will be destroyed at the latest 5 years after the final clinical study report (CSR). Details on sampling procedures, sample storage and shipment are given in the Sample Handling Manual.

Additional PK sampling at unscheduled visits is allowed at the discretion of the investigator for safety purposes (see Section 8.4).

Study treatment concentration information that may unmask the study, will not be reported to investigative sites or masked personnel until the study has been unmasked.

Any changes in the timing or addition of time-points for any planned study assessments must be documented and approved by the relevant study team member and then,

archived in the Sponsor and site study files, but this will not constitute a protocol amendment. The IRB/IEC will be informed of any safety issues that require alteration of the safety monitoring scheme or amendment of the ICF.

### **8.5.1 Aqueous Humor Samples (Optional)**

An optional aqueous humor sample will be collected from either eye receiving intravitreal rescue treatment with the therapies permitted in Section 6.5.1 and who provide additional consent to participate. Aqueous humor samples must not be collected from monocular participants. Where participants consent to aqueous humor sampling, all efforts should be made to collect a baseline aqueous humor sample prior to the administration of rescue treatment. Unscheduled sampling could be performed at other or additional planned visits at the discretion of the Investigator in agreement with the participant.

The aqueous humor sample (0.1 mL) should be collected by a qualified physician after all other assessments have been completed but before rescue therapy is provided as per Table 2 (Section 1.3), using an aseptic procedure and sterile field and according to local guidelines.

Determination of RG7774 (and its metabolite[s], as appropriate) concentration in aqueous humor for exploratory quantification purposes may be performed with the non-validated LC-MS/MS method(s). [REDACTED] identification, assay development purposes, and assay validation or compound-related assays after the mentioned intended use. These specimens will be destroyed no later than 5 years after the date of final CSR.

The informed consent form will contain a separate section that addresses the use of aqueous humor samples for optional exploratory biomarker research. A separate signature will be required to document a participant's agreement to allow this sample to be taken and used for exploratory research.

[REDACTED]

[REDACTED]

[REDACTED]

[REDACTED]

[Redacted]

[Redacted]

[Redacted]

[Redacted]

- [Redacted]
- [Redacted]
- [Redacted]

[Redacted]

[Redacted]

[Redacted]

[Redacted]

[Redacted]

[REDACTED]

[REDACTED]

[REDACTED]

### **8.7 PHARMACODYNAMICS AND BIOMARKER SAMPLES**

The samples may also be used for research purposes to identify biomarkers useful for predicting and monitoring response to RG7774, identifying biomarkers useful for predicting and monitoring RG7774 safety, assessing pharmacodynamic effects of RG7774, and investigating mechanism of therapy resistance. Additional markers may be measured in the case that a strong scientific rationale develops.

[REDACTED]

Based on continuous analysis of the data in this study and other studies, any sample type and/or analysis not considered to be critical for safety may be stopped at any time if the data from the samples collected does not produce useful information.

Unless otherwise specified below, samples (including blood, slides, extracts, etc.) will be destroyed no later than 5 years, and for genetics/ genomics samples up to 15 years, after the date of final CSR.

[REDACTED]

[REDACTED]

Details on processes for collection and shipment of these samples can be found in separate sample documentation.

[Redacted]

[Redacted]

[Redacted]

[Redacted]

[Redacted]

[Redacted]

[Redacted]

[Redacted]

- [Redacted]

- [Redacted]

- [Redacted]

- [Redacted]

- [Redacted]

[Redacted]

[Redacted]

- [Redacted]
- [Redacted]
- [Redacted]
- [Redacted]
- [Redacted]

[Redacted]

[Redacted]

[Redacted]

[Redacted]

[Redacted]

## **8.9 MEDICAL RESOURCE UTILIZATION AND HEALTH ECONOMICS**

This section does not apply to study BP41321.

### **8.10 TIMING OF STUDY ASSESSMENTS**

#### **8.10.1 Screening and Pre-treatment Assessments**

Written or electronic (eConsent) informed consent for participation in the study must be obtained before performing any study-specific screening tests or evaluations. Informed Consent Forms for enrolled participant and for participants who are not subsequently enrolled will be maintained at the study site.

All screening, and all pre-treatment assessments (related to entry criteria), must be completed and reviewed to confirm that participants meet all eligibility criteria. The Investigator will maintain a screening log to record details of all participants screened and to confirm eligibility or record reasons for screening failure.

At any study visit (including screening visit), each category of assessments (i.e., sample collection, imaging procedures, PROs, etc.) is recommended to be performed following the order specified in the SoA table (see Section 1.3).

Screening and pre-treatment assessments will be performed during 21 days, Day –28 to Day –7 prior to Day 1, unless otherwise specified, to allow for sufficient time to process samples and receive external eligibility reports.

#### **8.10.2 Assessments during Treatment**

Under no circumstances will participants who enroll in this study and have completed treatment as specified, be permitted to be allocated a new randomization number and re-enroll in the study.

All assessments must be performed as per SoA (see Section 1.3).

The Sponsor has included two visits to monitor if there is a need to adjust the dose of warfarin. These visits will take place 7 days after the first dose of the study treatment (on Day 7) and 7 days after the last dose of the study treatment (i.e. at around Week 37 for participants completing the treatment period and at individually determined time-points for participants discontinuing treatment or the study prematurely). The visits are required for all participants on warfarin and will include a blood test for clinical parameters of coagulation. The Investigator will communicate the results to the participant's regular diabetologist/ endocrinologist. All participants will be managed according to the best judgment of their treating physicians as informed by current local clinical practice guidelines and the best clinical evidence for patients with DR.

See also Sections [8.1](#) and [8.2](#) for further details.

### **8.10.3 Assessments at Study Treatment Completion / Early Termination Visit**

Participants who complete the 36-week treatment phase will be asked to return to the clinic for two visits with fewer assessments compared to the regular visits:

- A safety follow-up visit, 28 ( $\pm 7$ ) days after the final dose of study treatment (week 40 visit),
- An efficacy visit, 84 ( $\pm 7$ ) days after the final dose of study treatment (week 48 visit).

Participants who discontinue from the study treatment phase early, will have an early termination visit and be asked to return to the clinic 28 ( $\pm 7$ ) days after the final dose of study treatment for a safety follow-up visit.

- if the early termination visit occurs within 14 days of the last site visit, the list of assessments to be performed will be reduced.
- If the early termination visit happens more than 14 days after a site visit a complete set of assessments needs to be performed.

See Section [1.3](#) ([Table 2](#)), and Sections [8.1](#) and [8.2](#) for further details.

### **8.10.4 Follow-Up Assessments**

After the study completion/early termination visit, AEs should be followed as outlined in Sections [8.3.1](#) and [8.3.3](#).

### **8.10.5 Assessments at Unscheduled Visits**

Please see Section [1.3](#) for activities that are required to be performed in case of an unscheduled visit. Assessments (e.g., for safety or for PK/PD sampling purpose) performed in case of an unscheduled visit(s) are at the discretion of the investigator. Participants will be instructed to contact the investigator at any time if they have any health-related concerns. If warranted, participants will be asked to return to the clinic as soon as possible for an unscheduled safety assessment visit. Assessments performed at unscheduled safety visits are at the discretion of the investigator. It is recommended to perform ocular assessments on both eyes.

## **9. STATISTICAL CONSIDERATIONS**

### **9.1 STATISTICAL HYPOTHESES**

Denoted by  $p_k$  the proportion of participants with  $\geq 2$  step improvement in ETDRS DRSS from baseline at Week 36 measured in the study eye in treatment group  $k$  ( $k = 0$  for placebo and  $k = 1, 2$ , for low, and high dose, respectively), the hypotheses

$$p_0 = p_k, k = 1, 2,$$

will each be tested at the two-sided 10% level. Due to the exploratory dose finding nature of the study no adjustments for multiplicity will be made. Hypothesis testing will be performed using the framework of Generalized Estimating Equations (GEE), as it takes into account repeated measures within each participant and can provide unbiased effect estimates even if the correlation structure between measures is misspecified.

### **9.2 SAMPLE SIZE DETERMINATION**

A total of 135 participants are expected to be randomized 1:1:1 to the three groups (45 participants per group). Based on Fisher's exact test, assuming the proportion of participants with  $\geq 2$  step improvement in the ETDRS DRSS to be 15% for placebo and 40% to 45% under active treatment, 40 participants completing the study per group provide between 74% and 88% power based on a 2-sided significance level of 0.1. Allowing for about 10% of the participants randomized to not complete the study and hence not have an assessment of the primary endpoint at week 36, a total of 135 participants (45 participants per group) was selected to obtain 120 completers. If the rate of participants not completing the study is larger than 10%, the sample size may be increased beyond 135 participants with the aim of achieving approximately 45 completers per group.

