### **NUMBER OF PARTICIPANTS**

A total of 135 participants are expected to be enrolled in this study and will be randomized 1:1:1 to the three groups (45 participants per group). Based on Fisher's exact test, assuming the proportion of participants with  $\geq 2$  step improvement in the ETDRS DRSS to be 15% for placebo and 40% to 45% under active treatment, 40 participants completing the study per group provide between 74% and 88% power based on a 2-sided significance level of 0.1. Allowing for about 10% of the participants randomized to not complete the study and hence not have an assessment of the primary endpoint at week 36, a total of 135 participants (45 participants per group) was selected to obtain 120 completers. If the rate of participants not completing the study is larger than 10%, the sample size may be increased beyond 135 participants with the aim of achieving approximately 45 completers per group.

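### Does the optional increase to about 45 completers per group conflict with a sample size built on 40 completers per group?

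*Combined protocol and SAP*

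**What the plan says.** Section 9.2 sizes the trial by Fisher's exact test, taking the proportion with a DRSS improvement of two or more steps "to be 15% for placebo and 40% to 45% under active treatment". On that basis, "40 participants completing the study per group provide between 74% and 88% power based on a 2-sided significance level of 0.1". With about 10% not completing, "a total of 135 participants (45 participants per group) was selected to obtain 120 completers".

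Section 9.2 then adds a contingency. If non-completion is above 10%, "the sample size may be increased beyond 135 participants with the aim of achieving approximately 45 completers per group". The Number of Participants paragraph of the synopsis gives the same sizing and the same contingency, "with the aim of achieving approximately 45 completers per group", so the two places agree with each other.

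Section 9.1 sets the error rates: the two dose-versus-placebo hypotheses "will each be tested at the two-sided 10% level", and "Due to the exploratory dose finding nature of the study no adjustments for multiplicity will be made". The version 5 amendment rationale and Section 9.5 (Interim Analyses) say nothing about why the contingency names 45.

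**The concern.** A clause triggered by excess non-completion would normally restore the completer number on which the power rests, here 40 per group or 120 in total. This one aims at about 45 per group, or 135 in total, which is 12.5% higher (45/40 = 1.125). Because 45 is also the number randomised per group, it could be a carry-over from the wrong line.

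The rule also jumps at its trigger. At 10% non-completion the plan is content with about 120 completers; just above 10% it may seek 135. The target is a number the sponsor would act on, and an ethics committee might ask what justifies the additional participants. Each of them is asked for 36 weeks of study treatment and follow-up to Week 48. If 45 were simply wrong, some people would be enrolled without a stated need.

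**Working it through.** **Inputs.** From Sections 9.1 and 9.2: two-sided significance level 0.10 for each dose against placebo; response 15% on placebo and 40% or 45% on active; 40 completers per group; 1:1:1 allocation; 135 randomised; about 10% non-completion. Non-completion rates above 10% below are assumptions, since the documents give only the 10% figure.

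**1. The plan's own power and size.** Power by full enumeration of two independent binomials, rejecting when the two-sided Fisher p-value is at most 0.10:

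| Completers per group | 15% vs 40% | 15% vs 45% |
|---|---|---|
| 40 | 75.5% | 87.5% |
| 45 | 79.8% | 90.7% |

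The stated 74% and 88% are each within 2 points of the values at 40, so the power statement belongs to 40 completers. For the size, 40/(1 − 0.10) = 44.4, rounded up to 45 per group, and 3 × 45 = 135, which matches. At 10% non-completion, 45 × 0.90 = 40.5 completers per group are expected, so the base plan was not meant to yield 45.

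**2. What the contingency adds.** Number to randomise = 3 × ceil(completers per group/(1 − d)), where d is the non-completion rate:

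| d | For 40 per group | For 45 per group | Difference |
|---|---|---|---|
| 10% (plan) | 135 | 150 | 15 |
| 11% | 135 | 153 | 18 |
| 12% | 138 | 156 | 18 |
| 15% | 144 | 159 | 15 |
| 20% | 150 | 171 | 21 |

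The gain in power is 79.8 − 75.5 = 4.3 points at a 40% response and 90.7 − 87.5 = 3.2 points at 45%.

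**3. Whether 40 would be the better target.** On expected totals, 135 randomised still gives 120 completers up to 1 − 120/135 = 11.1% non-completion, which suggests that no increase is needed before then. But the power statement is per group, and an expected count of 40 leaves a sizeable chance of fewer. Assume independent binomial non-completion at the same rate in each group:

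| Randomised per group | d | P(one group reaches 40) | P(all three reach 40) |
|---|---|---|---|
| 45 | 10% | 71% | 35% |
| 45 | 11.1% | 62% | 23% |
| 50 | 10% | 99% | 97% |

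The last column is the cube of the unrounded single-group probability. Randomising for an expected 45 therefore makes 40 in every group close to certain at 10% non-completion. Randomising for an expected 40 does not.

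**The case for a change.** The strongest case for a change is that Section 9.2 contains a single chain of reasoning (40 completers, 10% loss, 135 randomised) and then a target that does not come from it. The words that make the clause permissive govern whether to increase and how closely to hit the target; they do not explain why it lies above the stated basis. At 11% non-completion the clause would allow recruitment to 153 although 135 would still be expected to give 120 completers. Correcting the figure, or adding its power, would take one sentence in two places.

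Much of this stands. The quotation is exact, the arithmetic holds, and no reason or power for 45 appears in the documents. What does not stand is the step from an unexplained figure to a wrong one. The two statements concern different things: the basis of the planned size, and an aim if losses are higher than planned. Both can be true. Nothing says the contingency is meant only to restore 40. A deliberate aim at roughly 80% to 91% power, or a margin so that each group reaches 40, would fit equally well; the documents do not settle which.

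Nor is either change a clear gain. Lowering the target to 40 would save participants but give up 3 to 4 points of power and the per-group margin, and a note that nothing is needed below 11.1% would hold only for the expected total. Keeping 45 and adding its rationale would leave the conduct and analysis of the trial as they are.

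**Conclusion.** No change is called for. The contingency target is an unexplained but harmless choice in an exploratory trial. It creates no bias, does not touch the 10% level of either comparison, and cannot lower power. Used in full, it costs about 15 to 21 participants beyond the number needed for an expected 40 completers per group, over non-completion of 10% to 20%, and in return gives power of about 80% to 91% instead of about 75% to 87%. A reader who wants the power at 45 can compute it from the inputs already in Section 9.2.

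This rests on the plan's own response rates, on Fisher's test applied to completers as the sizing approximation (the primary analysis in Section 9.4.2 is a GEE using all visits in the ITT population), on assumed non-completion rates above 10%, and, for the chance that each group reaches 40, on independent binomial losses. If the sponsor knows that 45 was typed for 40, it is a clerical slip to correct when the text is next opened. The documents do not show that, and following the plan as written gives sound results.

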## 9.3 POPULATIONS FOR ANALYSES

For purposes of analysis, the following populations are defined in [Table 6](#).

